8.1.10 Unanticipated Problem that is not an Adverse Event (UPnonAE)

This is an unanticipated problem that does not fit the definition of an AE, but which may, in the opinion of the investigator, involve risk to the subject, affect others in the research study, or significantly impact the integrity of research data. Such events would be considered non-serious unanticipated problems. For example, we will report occurrences of breaches of confidentiality, accidental destruction of study records, or unaccounted-for study drug.

8.1.11 Protocol Deviation

A protocol deviation is any change, divergence, or departure from the study design or procedures in an IRB-approved research protocol that has an impact on the subject's rights, safety, or well-being, and/or the completeness, accuracy, or reliability of the study data. Protocol deviations are designated as serious or non-serious and further characterized as:

1. Those that occur because a member of the research team deviates from the protocol

2. Those that are identified before they occur, but cannot be prevented
3. Those that are discovered after they occur

8.1.12 Serious Protocol Deviation

A serious protocol deviation is any change, divergence, or departure from the study design or procedures in an IRB-approved research protocol that meets the definition of a Serious Adverse Event or compromises the subject's rights, safety, or well-being, and/or the completeness, accuracy, or reliability of the study data.

Non-compliance is the failure to comply with applicable NIH Human Research Protection Program (HRPP) policies, IRB requirements, or regulatory requirements for the protection of human subjects. Non-compliance is further characterized as

1. Serious: Non-compliance that:
 - a. Increases risks or causes harm to subjects
 - b. Decreases potential benefits to subjects
 - c. Compromises the integrity of the NIH HRPP
 - d. Invalidates the study data
2. Continuing: Non-compliance that is recurring
3. Minor: Non-compliance that is neither serious nor continuing

8.1.13 Pre-existing Conditions, Worsening of Pre-existing Condition

Stable chronic conditions that are present prior to enrollment and do not worsen are not considered AEs and will be accounted for in the subject's medical history. Exacerbation or worsening of pre-existing conditions are defined as AEs and are evaluated using the same criteria described in Section 8.2 of this protocol.

8.2 Assessment of Adverse Events

8.2.1 Identification of Adverse Events

All AEs occurring from the time the subject is enrolled (at administration of investigational agent on day 0) through the Study Day 28 will be documented, recorded, and reported. The Investigator will assess all AEs with respect to **Seriousness**, **Severity**, and **Causality** (relationship to study agent and relationship to research) according to the following guidelines. An assessment of safety will include clinical observations and monitoring of hematological, blood chemistry, and immunologic parameters. Safety will be evaluated by monitoring the subjects for local and systemic adverse events during the course of the trial. Subjects will be closely monitored for 30 minutes following inoculation. Additionally, subjects will return to the clinic on study days 4, 6, 8, 10, 12, 14, 16, 21, and 28 post-inoculation and may be asked to return more often if warranted. It is during this time period that we anticipate AEs related to infection with the vaccine virus to manifest themselves; therefore, the subjects will be seen frequently. Study staff will review subjects' reported temperatures and clinical temperatures for the first 16 days following inoculation to assess for AEs. At each visit through study day 28 following inoculation, subjects will be queried about adverse events, including possible vaccine-related AEs (solicited AEs) and will have a focused physical exam performed. A study clinician will be available to subjects by telephone or pager 24 hours a day during the study evaluation period.

All AEs will be recorded during the period after the subject receives the study vaccine through and including post-inoculation study day 28.

All SAEs will be assessed appropriately as AEs and reported following SAE reporting guidelines outlined in Section 8.3.2 of this protocol.

8.2.2 *Protocol Specific Adverse Event Definitions*

Fever: Temperature $\geq 100.4^{\circ}\text{F}$ lasting at least 1 hour

ZIKV-like Rash: Areas of **confluent** macular or maculo-papular rash over trunk and extremities, blanches when compressed.

Non-purulent conjunctivitis: Bilateral reddening of the sclera of the eyes without evidence of exudate or crusting of the eyelids

Headache: A pain located in the head, over the eyes, at the temples, or at the base of the skull.

ROP: Bilateral pain situated behind the orbits of the eye

Photophobia: An abnormal sensitivity or intolerance to light

Nausea: Discomfort in the stomach with an urge to vomit

Fatigue: Excessive tiredness following minimal exertion

Myalgia: Pain in the muscles that is found in ≥ 2 muscle groups

Arthralgia: Pain in a joint that is found in ≥ 2 joints.

Muscle Weakness: Grade 0 - 3 out of 5 on the Oxford Scale. The Oxford Scale grading is as follows:

- **0/5:** No contraction
- **1/5:** Visible/palpable muscle contraction but no movement
- **2/5:** Movement with gravity eliminated
- **3/5:** Movement against gravity only
- **4/5:** Movement against gravity with some resistance
- **5/5:** Movement against gravity with full resistance

8.2.3 *Determination of Severity*

The investigator/designee will assess all AE severity using the following classifications.

Table 10: Severity Definitions

Severity	Defined
Grade 1 (Mild)	An event that is easily tolerated and may require 1 dose of medication/treatment
Grade 2 (Moderate)	An event that interferes with daily activity or requires > 1 dose of medication/treatment
Grade 3 (Severe)	An event that prevents daily activity and requires medical intervention
Grade 4 (Life-threatening)	An adverse event that is deemed by the study clinician, the medical monitor, or an outside clinician caring for the subject to be life-threatening
Grade 5 (Death)	Any adverse event that results in the death of the subject

Solicited AE severity grading classifications are listed in Table 10 and

Table 11. All other AEs will be graded on severity using the Adverse Event Grading Table in Section 14.1, Appendix I.

Table 11: Assessment of Solicited Adverse Events

Local Reactogenicity	Grade	Severity
Injection Site Tenderness, Pruritis, and Pain	1	An event that is easily tolerated and may require 1 dose of medication
	2	An event that interferes with daily activity or requires > 1 dose of medication
	3	An event that prevents daily activity and requires medical intervention
	4	A life-threatening event
Injection Site Induration and Erythema	1	> 0 – 20 mm
	2	> 20 – 50 mm
	3	> 50 mm
	4	Life-threatening
Systemic Reactogenicity	Grade	Severity
Fever (Oral)	1	100.4°F – 101.4°F
	2	101.5°F – 102.4°F
	3	≥ 102.5°F
	4	Life-threatening
ZIKV-Like Rash	1	A rash that is present but asymptomatic
	2	A rash that is symptomatic (pruritus/pain) but does not interfere with function
	3	A rash that is symptomatic and interferes with function
	4	A rash that is life-threatening
Headache	1	An event that is easily tolerated and may require 1 dose of medication/treatment
ROP		
Photophobia	2	An event that interferes with daily activity or requires > 1 dose of medication/treatment
Nausea		
Fatigue	3	An event that prevents daily activity and requires medical intervention
Myalgia		
Arthralgia	4	A life-threatening event
Conjunctivitis		
Muscle weakness		
Solicited Laboratory AEs	Grade	Severity
Hemoglobin (Women)	1	9.5 – 10.7 gm/dL
	2	8.0 – 9.4 gm/dL
	3	< 7.9 gm/dL
	4	Life-threatening
Hemoglobin (Men)	1	11 – 12.5 gm/dL
	2	9.0 – 10.9 gm/dL
	3	< 8.9 gm/dL

	4	Life-threatening
Neutropenia (Reduced ANC)	1	750 – 999/mm ³
	2	500 – 749/mm ³
	3	< 500 mm ³
	4	Life-threatening
Leukocytosis (Increased WBCs)	1	11,500 – 13,000/mm ³
	2	13,001 – 15,000/mm ³
	3	15,000 or < 1,000/mm ³
	4	Life-threatening
Thrombocytopenia (Decreased Platelets)	1	≥ 100,000 – 120,000/mm ³
	2	≥ 75,000 – 99,999/mm ³
	3	< 74,999/mm ³
	4	Life-threatening
ALT	1	> 1.25 – 2.5 × ULN
	2	> 2.5 – 5.0 × ULN
	3	> 5.0 × ULN
	4	Life-threatening

1. Any adverse event resulting in death will be given a severity grade of 5.

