- 1) Assess the frequency, quantity, and duration of viremia after a single dose of rZIKV/D4Δ30-713 given at either 10^3 PFU or 10^4 PFU.
- 2) Evaluate the number of vaccine recipients infected with either 10^3 PFU or 10^4 PFU rZIKV/D4Δ30-713. Infection is defined as recovery of infectious vaccine virus from the blood, serum, or urine of a subject and/or by seroconversion to ZIKV (plaque-reduction neutralization titer [PRNT₅₀] $\geq 1:10$) within the 90-day period following vaccination.
- 3) Determine the durability of antibody response 26 weeks after vaccination.
- 4) Determine the quantity and duration of ZIKV presence as determined by:
 - The peak virus titer in the blood and the duration of viremia induced by the LA Zika vaccine as determined by RT-PCR and virus culture
 - The quantity and duration of possible Zika vaccine shedding in urine determined by RT-PCR and virus culture
 - The quantity and duration of possible Zika vaccine shedding in vaginal secretions determined by RT-PCR and virus culture
 - The quantity and duration of possible Zika vaccine shedding in semen determined by RT-PCR and virus culture

Exploratory objectives:

- 1) To evaluate the phenotype of peripheral blood mononuclear cells (PBMCs) at primary infection with the rZIKV/D4Δ30-713 vaccine.
- 2) To evaluate the cellular immune response to primary infection with the rZIKV/D4Δ30-713 vaccine.
- 3) To evaluate the innate immune response to primary infection with the rZIKV/D4Δ30-713 vaccine.
- 4) To evaluate B and T cell memory responses following primary infection with the rZIKV/D4Δ30-713 vaccine.
- 5) To evaluate the antibody response in saliva to infection with rZIKV/D4Δ30-713 as a possible diagnostic tool. This will be done in a subset of subjects (those enrolled at the Center for Immunization Research [CIR]).

Primary Endpoints

Safety

Occurrence, intensity and relationship to vaccination of solicited local and general adverse events (AEs) within the 28-day follow-up period after vaccination.

Occurrence, intensity and relationship to vaccination of unsolicited AEs within the 28-day (Days 0-28) follow-up period after vaccination.

Occurrence of medically-attended adverse events and serious adverse events (SAEs) throughout the entire study period.

Immunogenicity

Determination of the peak neutralizing antibody titer to ZIKV through 90 days following vaccination with either 10^3 PFU or 10^4 PFU of rZIKV/D4 Δ 30.

Secondary Endpoint

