4. Perform interim history, including sexual history, and focused physical exam, concentrating on any acute complaints. Focused physical exam will include BP, HR, temperature, respiratory rate, skin examination, eyes, throat, muscle strength, and biceps and patellar deep tendon reflexes. Physical exam may extend beyond these if indicated by complaint or physical finding.
5. Review and document concomitant medications.
6. Nasopharyngeal (NP) or mid-turbinate swab to test for SARS-CoV 2 – the virus that causes COVID-19 – will be collected based on guidance from federal, state, local, and/or institutional health officials* or at the discretion of the clinician (*may be obtained up to 72 hours in advance of study day*).

*This guidance may be informed by the local COVID infection rate, severity of infections, vaccination rates, and other factors as the COVID-19 pandemic continues to evolve and change.

7. Obtain approximately 70 mL of blood for CBC with differential, ALT, creatinine, virus isolation and culture (PCR/culture), and immunology (PBMCs, plasma, and PAXGene). These laboratory studies are drawn as baseline values and will not determine eligibility.
8. Obtain 5 mL of clean-catch urine for virus isolation & culture.
9. Obtain vaginal secretion sample (women) for virus isolation and culture (may be collected at home by the volunteer).
10. Obtain semen sample (men) for virus isolation and culture (may be collected at home by the volunteer).
11. Obtain oral fluid for serology (CIR site only).
12. Perform serum or urine β -HCG testing for female subjects. Ensure the test is negative before proceeding; a positive test will exclude the subject from the study as per protocol, Section 5.2.
13. Review pregnancy prevention.
14. Record vital signs (blood pressure, temperature, heart rate, and respiratory rate).
15. Administer the test article.
16. Observe for at least 30 minutes after inoculation and evaluate for immediate hypersensitivity.

17. Provide education by study staff describing proper use of thermometer, the signs and symptoms of potential AEs, and how and when to contact study staff (see Section 7.5.1).

Study Day 4 (± 1 day)

1. Screening questions for COVID-19.
2. Perform interim history and focused physical exam, concentrating on any acute complaints.
3. Record vital signs.
4. Obtain approximately 40 mL of blood for CBC with differential, virology, and immunology (PBMCs, plasma, and PAXGene).

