7.5 Subject Temperature Memory Card

Subjects will be provided with a thermometer and a Temperature Memory Card to use as a memory aid and will be asked to record temperatures 2 times a day from study day 0 through study day 16 post-inoculation. Study staff will review the subjects' temperature cards on study day visits 4 through 21 to assess for any fevers and compare subject recordings to the study visit temperatures. Staff will record all temperatures recorded by the subject and will also separately record the maximum temperature for each date (T_{max}) on the source document. Subject memory cards will not be collected by the study staff as subject's recordings will not be considered required data.

Staff will instruct subjects on how to use the thermometers, to take their temperatures at approximately the same time each day, and to take additional temperatures if they feel they have elevated temperatures. Subjects will be asked to wait at least 15 minutes after eating, drinking, and smoking before taking their temperatures. They will be asked to confirm an elevated temperature ($\geq 100.4^{\circ}\text{F}$) by retaking the temperature after a 20-minute interval and at 1 hour. Temperatures not documented to last at least 1 hour will not be considered an AE or included in the analysis.

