7.5.1 Notification of Staff of Zika-like Symptoms

Subjects will be asked to call or otherwise contact the study staff should they experience any symptoms of Zika illness. The Zika-like illness symptoms that study staff will review with the subjects are the systemic reactogenicity signs included in [Table 9](#). Once notified, study staff will arrange to evaluate the subject at the earliest convenience; this may result in an unscheduled visit for the subject.

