11.4.4 Inoculation

Possible local vaccine reactions include pain, swelling, or erythema for 2 to 3 days, lymphadenopathy, or pruritus at the injection site. Potential systemic reactions that may occur include symptoms of ZIKV such as rash, fever, headache, non-purulent conjunctivitis, generalized myalgias, and arthralgias. Immediate hypersensitivity reactions including urticaria, anaphylaxis, or other IgE-mediated responses are possible, as with any vaccine. Guillain-Barre syndrome has been reported in persons infected with wt ZIKV.

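### Between the 30-minute observation and the Day 4 (±1) visit, local reactions are ascertained by recall only, so erythema and induration that resolve in that interval cannot be graded by size

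*Combined protocol and SAP*

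**What the plan says.** The Precis lists as a primary safety endpoint: "Occurrence, intensity and relationship to vaccination of solicited local and general adverse events (AEs) within the 28-day follow-up period after vaccination". Table 9 names five local terms: pain, erythema, tenderness, induration and pruritus. Section 10.3 asks for local reactions to be assessed separately from systemic ones, and Section 8.2.4 counts every injection-site reaction as causally related.

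Table 11 grades tenderness, pruritus and pain by effect on daily activity and need for medication. It grades induration and erythema by size, with cut-points at 20 mm and 50 mm, apart from the life-threatening grade. Appendix 1 uses the same size bands.

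On duration, Section 11.4.4 says: "Possible local vaccine reactions include pain, swelling, or erythema for 2 to 3 days, lymphadenopathy, or pruritus at the injection site".

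On collection:
- Section 7.4.1, Day 0: "Observe for at least 30 minutes after inoculation and evaluate for immediate hypersensitivity". The next visit is Day 4 with a window of one day either side.
- Section 7.5: subjects "will be asked to record temperatures 2 times a day from study day 0 through study day 16 post-inoculation". Staff transcribe the readings, but the card is not collected and its entries are not required data.
- Section 7.5.1, on when to contact staff: "The Zika-like illness symptoms that study staff will review with the subjects are the systemic reactogenicity signs included in" Table 9. The local column is not mentioned.
- Section 8.2.1: "subjects will return to the clinic on study days 4, 6, 8, 10, 12, 14, 16, 21, and 28 post-inoculation". At every visit through Day 28 subjects are asked about solicited events and given a focused examination. A clinician can be reached by telephone at any hour.

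Halting criterion 4 in Section 8.5.1.1 counts two or more subjects with the same related Grade 3 objective finding. It excepts injection-site erythema but not induration.

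**The concern.** The schedule in Section 8.2.1 is justified by when events from vaccine-virus infection are expected. Injection-site reactions follow a different clock. If they last about as long as Section 11.4.4 describes, many that start soon after the injection will be over before anyone examines the arm. No record made at the time would exist.

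Two things are at stake. First, intensity is a named part of the primary endpoint, and for erythema and induration it depends on a measurement. A subject cannot supply a diameter from memory for a lesion that has gone. For the same reason, halting criterion 4 has no scheduled measurement behind it for induration above 50 mm that resolves early. Second, because all local reactions count as related, any that are forgotten or not mentioned drop out of the adverse-reaction count under Primary Objective 1.

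**Working it through.** **The plan's own figure.** Table 7 has one non-zero local row: erythema in 1/20 vaccine and 0/8 placebo recipients, one-sided P = 0.7143. With a single event among 28 subjects, the one-sided Fisher exact probability is 20/28 = 0.7143, so the figure reproduces. Tenderness, pain, pruritus and induration are zero in both groups.

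**Timing.** Inputs: duration d of 2 or 3 days (Section 11.4.4); first visit v on Day 3, 4 or 5 (Section 7.4.1). Onset day o is not given, so Days 0, 1 and 2 are tried. A reaction is present at the visit if o ≤ v < o + d, or on a more generous inclusive count if o ≤ v ≤ o + d.

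| Onset | Duration | Day 3 visit | Day 4 visit | Day 5 visit |
|---|---|---|---|---|
| Day 0 | 2 days | gone | gone | gone |
| Day 0 | 3 days | inclusive only | gone | gone |
| Day 1 | 2 days | inclusive only | gone | gone |
| Day 1 | 3 days | present | inclusive only | gone |
| Day 2 | 2 days | present | inclusive only | gone |
| Day 2 | 3 days | present | present | inclusive only |

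A Day 0 reaction of the stated length is gone at the nominal visit on either count. Later onset leaves some reactions visible. The stated duration attaches to pain, swelling and erythema; applying it to induration treats swelling as its nearest equivalent, which is an assumption.

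**Grading.** Three of the five terms (pain, tenderness, pruritus) use criteria a subject can report afterwards. Two of the five (erythema, induration) need a size.

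**What the Cohort 1 zeros can bear.** The exact two-sided 95% upper limit for 0/20 is 1 − 0.025^(1/20) = 0.168. For 1/20 the interval is 0.1% to 24.9%. These limits reflect sampling error only. Let s be the share of true reactions that get recorded. The documents give no value, so s is assumed over a range. The upper limit on the true rate becomes 0.168/s, and the chance of seeing 0/20 when the true rate is 20% is (1 − 0.20s)^20.

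| Assumed capture s | Upper limit behind 0/20 | Chance of 0/20 if true rate is 20% |
|---|---|---|
| 100% | 17% | 1% |
| 80% | 21% | 3% |
| 50% | 34% | 12% |
| 30% | 56% | 29% |

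**Effect on the vaccine-placebo contrast.** If capture is equal in the blinded arms, the recorded difference is s × (vaccine rate − placebo rate). It shrinks in proportion to s but does not vanish unless s is zero.

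**The case against.** The strongest reply is that a missing diary is not missing ascertainment. Section 8.2.1 requires all events from administration onward to be recorded and solicited events to be queried at each visit, so the Day 4 history covers the preceding days. Subjects are taught on Day 0 what to look for, can call at any hour, and may have the site photographed (Section 7.4). The same questioning in Cohort 1 produced headache in 50%, fatigue in 25% and one erythema, so the system does pick up events. Section 11.4.4 is a list of possible risks with no onset time, and the study is descriptive.

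Much of this stands, and it rules out several stronger readings. A reader might infer that most local reactions are missed or cannot be graded. The documents give no capture rate, three of the five terms can be graded from recall, and later-onset reactions can persist to the visit. A reader might infer that any vaccine-placebo difference is hidden; equal under-capture only attenuates it. A reader might also infer that the Table 7 zeros are an artefact, or that they drove the move to the second dose. The zeros fit low reactogenicity equally well, and Sections 2.3.3 and 4.1 attribute Cohort 2 to insufficient infectivity and seroconversion.

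None of the reply supplies a diameter for erythema or induration that has already gone. The Day 0 teaching on contacting staff refers to Section 7.5.1, which lists systemic signs. Photographs are optional. A subject positive for SARS-CoV-2 in the first 21 days may be seen by telehealth, without an in-person examination.

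**Conclusion.** The point holds in a limited form. From the end of the 30-minute observation until a visit on Day 3, 4 or 5, local reactions are ascertained by recall. Erythema and induration that resolve in that interval cannot be graded by measured size as Table 11 requires. The intensity part of the primary local endpoint is therefore not reliably obtained for two of five terms, and halting criterion 4 has the same weakness for induration. Rates of all five terms may be under-recorded; how far is unknown, and the capture table illustrates this under assumed values and is not an estimate.

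The conclusion rests on the duration in Section 11.4.4 and on onset soon after injection. It is a modest defect in a descriptive study, but it touches a primary endpoint and is cheap to repair.

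**What to change.** In Section 7.5, add the five Table 9 local items to the existing card, once daily for Days 0 to 7, with erythema and induration measured in millimetres using a supplied ruler. State that these entries are required data, to be transcribed and graded by staff at the Day 4, 6 and 8 visits; without that change the present wording on card entries would undo the repair. Add local reactions to the contact instruction in Section 7.5.1. On Day 0, record an injection-site check at the end of the 30-minute observation.

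In the analysis, compare Cohort 2 local rates with that cohort's own placebo recipients and not directly with Cohort 1. Describe Cohort 1 local rates as collected by visit-based recall only if the protocol version then in force confirms it, since that version is not among the documents.

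The cost is a short amendment, a ruler, a few lines on a card already issued, and a small daily task for subjects. No visit is added. The real downside is that local ascertainment becomes more sensitive in Cohort 2 than in Cohort 1. Local comparisons then rest on 8 concurrent placebo recipients, for whom even 0/8 has an exact 95% upper limit of 36.9%.
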